# The research plan

## 1, and the study background

Protective constraints, also known as physical constraints, the US Bureau of Health care (HCFA) defines it as "with any physical or mechanical equipment, materials or tools attached to or adjacent to the patient's body, so that patients can not easily remove it, in order to limit the free movement of patients or the normal access to their own body". In order to avoid risks such as unplanned extubation and ensure patient safety, the majority of ICU caregivers believe that protective constraint is one of the important measures for the safety management of ICU patients. Therefore, protective constraint has become a common nursing problem in intensive care units at home and abroad. At the same time, with the deepening of humanistic concepts, protective constraints are also getting more and more attention. In 2003, the American Association of Critical Care Medicine developed the clinical implementation guidelines for the technical evaluation of restraint necessity levels, in order to ensure the physical and mental health of ICU patients. In 2004, the British Association of Critical Care Nurses developed practical guidance for adult protective constraints in intensive care units, stating that protective constraints are optimal patient care and should not replace inadequate human resources as one of the routine care measures in the ICU. In 2016, the Nursing Center of the National Institute of Health and Family Planning Hospital Management in China included the "physical constraint rate of hospitalized patients" in the Practical Manual of Nursing Sensitive Quality Indicators, aiming to reduce the overuse of protective constraints in ICU patients.

Constraint equipment refers to the self-injury, may hurt others and patients to limit the activities of the body or a part of the body, in order to achieve the maintenance of the safety of patients, to ensure the smooth treatment, nursing of all kinds of appliances. The essence of the constraint appliance is to limit patient activity to reduce the risk of unexpected adverse events. With the in-depth implementation of quality nursing services, nurses are also paying more

Version 2022.01 Version 1

and more attention to restraint nursing, and developed a variety of restraint appliances. Common restraint appliances include bed bars, wrist or ankle restraint belt, restraint vest, shoulder belt or belt type restraint belt, mittens, etc. According to the limitations of traditional restraint appliances, Deng Wandi et al. innovatively made double insurance restraint belt, racket gloves and safety vest. The research results showed that the innovative new restraint appliances can effectively reduce the psychological pressure of nurses and improve the complications caused by restraint. Xu Yan according to the characteristics of severe patients on the basis of the original constraint appliance innovation made safety protection three-piece set of constraint appliance, the appliance consists of safety constraints vest, gloves and knee constraints, the results show that the new constraint appliance can effectively reduce constraints of adverse events, improve family satisfaction.

In view of the above problems, the department developed a new protective restraint device, which is used for the protective restraint of postoperative intubation patients, and summarized nursing experience to provide clinical reference and theoretical basis for standardizing postoperative patient restraint. This project is now a general scientific research project of Zhejiang Provincial Department of Education. The project name is "Research on the Application of New restraint appliance in the Safety Management of Patients after cardiac surgery", and the funding source is

Self-raised.

## 2, and the study purpose

According to the individual characteristics of ICU patients, combined with the needs of patients, the innovative production of a new restraint appliance and study the effectiveness and safety of the new restraint appliance, to provide clinical reference and theoretical basis for the standardization of postoperative patient restraint.

#### 3. Study design and method:

3.1 This study used random number table to divide the subjects into control and experimental groups.

3.2 The research period of the whole project starts from the date of ethical passage and ends in 2024.

3.3 Inclusion criteria: ① elective surgery patients, age 18; ② preoperative awareness and no communication impairment; ③ open heart surgery under intravenous or inhalation general anesthesia; ④ ICU\_During the treatment, endotracheal intubation existed; before ⑤ restraint, there was no joint dysfunction, edema, skin damage, etc. at the proposed restraint site, and the peripheral circulation was good;
⑥ gave informed consent to participate in this study. Exclusion criteria: ① had a history of mental illness; ② had bleeding tendency or skin disease; voluntary abandonment of treatment or death in ③.

3.4 Sampling strategy and grouping: This study used the convenient sampling method to select the research subjects, and then the included subjects were randomly divided into control group and experimental group according to the coin throwing method. The control group used the restraint appliance as the sponge restraint belt, and the experimental group used the restraint appliance as the new restraint appliance.

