## 3.5 Interventions:

3.5.1 Control group: sponge restraint band, restraint method: adjust the fixed wrist band according to the wrist diameter of the patient's hand (foot), and then circle the fixed band around the wristband, one end of the puncture hole without tying, and the two ends of the fixed band are fixed on both sides of the bed as needed.

3.5.2 Experimental group: new restraint appliance, which is an adjustable protective restraint device (patent No. ZL202020155913.1), including upper bracket 1, upper bracket 2, lower bracket 2 and gloves; the multiple fixed supports are provided with air holes and breathable cotton to increase air permeability and comfort. Place the patient's elbow with the lower fixed bracket one and two, and then connect the upper fixed bracket one and the upper and lower fixed bracket two, and adjust the tightness, and the other to form a removable and rotating connection in a certain angle range to adjust the movement angle of the patient's elbow joint; set the patient's hand with the palm of the glove. The device was commissioned by Anshan Deyi Da Medical Device Technology Co., LTD. (Business license registration number: 912103003966197061, class I medical device production record No.: Liaoan Food and Drug Device Production Preparation 20200011).

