## 3.6, Outcome measures

.13.6 Outcome decision time

This study starts with the use of the protective restraint tool after surgery until the removal of the endotracheal tube..23.6 Main outcome measures

I Adverse event rate of nursing care:

Unplanned extubation rate: unplanned extubation includes a self-extubation without the consent of medical staff; b. Pipeline slip caused by various reasons; c. Extubation needs to be performed in advance due to catheter quality problems and catheter blockage. Unplanned extubation rate = number of unplanned extubation cases in the same period / total number of ICU inpatients in the statistical period 100%. .73 Data collection

Data were collected by on-site assessment and medical record review. General demographic data including age, gender, education, marital status, occupation, smoking, alcohol consumption, health insurance type, surgical mode, admission diagnosis, history of underlying diseases, were collected by the investigator by medical record review. The incidence of nursing adverse events, duration of restraint period, cumulative dose of sedation used, length of ICU stay, and total cost of ICU treatment were collected by the investigator through the electronic medical system and integrated nursing information platform before pre-transfer to the ICU. Anxiety, depression and comfort were assessed by the responsible nurse within 24h after the patient woke from anesthesia and on the day the patient was pre-transferred out of the ICU.

.83 Quality control

.8.13 The hospital has established a unified and standardized restraint process, and will regularly regular restraint and skin care training for nurses.

.23.8 Each class has a responsible leader, who will check the skin assessment and the rigor of nursing records, and ensure the quality of nursing records.

3.8.3 Double verification during data collection and entry.

.93 Statistical analysis

.0 Statistical analysis by SPSS 25 software, frequency and percentage for count data, chi-square test or Fisher test for between-group comparison, mean  $\pm$  standard deviation for normal distribution data, t-test for groups, non-normal distribution data, and non-parametric test for between-group comparison. A P <0.05 was considered as a statistically significant difference.

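### Section 3.6 opens the main-outcome window at use of the restraint tool, a moment that follows allocation and depends on the arm, and criterion ④ does not say when the tube must be present

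*Protocol*

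**What the plan says.** Three parts of the protocol bear on timing.

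- **Eligibility (section 3.3, criterion ④).** In the ICU, "During the treatment, endotracheal intubation existed". No time point is attached. Criterion ⑤ is judged before restraint: before "restraint, there was no joint dysfunction, edema, skin damage, etc. at the proposed restraint site".
- **Allocation (section 3.4).** After convenience sampling, "the included subjects were randomly divided into control group and experimental group according to the coin throwing method". The control group receives the sponge belt and the experimental group the new appliance. The section does not say whether this happens before surgery, on ICU arrival or later.
- **Outcome window (section 3.6, outcome decision time).** "This study starts with the use of the protective restraint tool after surgery until the removal of the endotracheal tube".

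The main outcome is the unplanned extubation rate, defined in section 3.6 as "number of unplanned extubation cases in the same period / total number of ICU inpatients in the statistical period". The statistical period is not defined.

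**The concern.** In a randomised comparison, follow-up for the main outcome should start at a moment that does not depend on the arm. Here it starts at an act that belongs to the arm: putting on the assigned appliance. The two appliances look different, so the staff who start the clock know the allocation, and the protocol sets no reference moment against which the delay could be checked.

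A tube lost between allocation and tool use falls outside the window on its literal wording. If that interval has the same length and risk in both arms, the risk ratio is unaffected. If one appliance takes longer to apply, its arm loses more early events from the count and looks better than it is. Time to application is part of what distinguishes two restraint appliances, so a window that starts at tool use removes a possible disadvantage of the slower one from the result.

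Because ④ has no time anchor, the text also does not exclude a patient whose tube is already out when the tool would be applied.

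**Working it through.** **1. Order of events.** The protocol does not state the order, but it can be deduced. Section 3.4 makes the tool a consequence of the arm, so the assigned tool cannot be in use before allocation. The section 3.6 window therefore opens after allocation, at a moment that may differ by arm.

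**2. Is unequal delay plausible?** In section 3.5.1 the belt requires a wrist band to be sized, a second band to be passed round it and through a hole, and both ends to be fixed to the bed. In section 3.5.2 the new appliance requires staff to "connect the upper fixed bracket one and the upper and lower fixed bracket two, and adjust the tightness", set the elbow angle and put on a glove. Both procedures have several steps, and no time is given for either. A difference is possible, but its size and sign cannot be read from the text.

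**3. Size under assumed inputs.** The protocol gives no event rate, fitting time or tube time, so there is no figure to reproduce. Suppose both arms have the same true risk. Let g_E and g_C be the shares of events that fall before tool use in the experimental and control arms. The true risk cancels:

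observed risk ratio = (1 − g_E) / (1 − g_C)

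Assume 10 hours with a tube, constant hazard, no delay in the faster arm, and 0.25 to 0.5 hours in the slower arm. The uncounted share in the slower arm is 0.25/10 = 2.5% to 0.5/10 = 5%.

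| Assumption | g_E | g_C | Observed risk ratio (true value 1) |
|---|---|---|---|
| Equal loss | 10% | 10% | 1.00 |
| New appliance 15 min slower | 2.5% | 0% | 0.975 |
| New appliance 30 min slower | 5% | 0% | 0.95 |
| Belt 15 min slower | 0% | 2.5% | 1/0.975 = 1.03 |
| Belt 30 min slower | 0% | 5% | 1/0.95 = 1.05 |
| Much larger early loss, new appliance | 20% | 5% | 0.80/0.95 = 0.84 |
| Much larger early loss, new appliance | 20% | 0% | 0.80 |

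The last two rows need an early concentration of events for which the documents give no evidence.

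**4. Patients without a tube at tool use.** Whether there would be any is unknown. For scale, if an assumed share f in each arm cannot have an event, both rates shrink by (1 − f) and the risk ratio is unchanged. The cost is power. For assumed rates of 10% and 2%, two-sided 0.05 and 80% power (normal approximation, pooled variance under the null), the number per arm is 138 at f = 0, 145 at f = 5% and 154 at f = 10%.

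**5. Planned tube removal before tool use.** Such a patient has no event whether the window starts at allocation or at tool use, and is among the randomised patients either way. This is not a second bias that a changed start would remove.

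**The case against.** The strongest reply is that the intent is clear and the gap trivial. The background section describes the device as one "which is used for the protective restraint of postoperative intubation patients". Criterion ⑤ looks ahead to restraint, and the window presupposes a tube in place when the tool goes on. Criterion ④, in a terse translation, can equally mean that a tube is present during ICU care. Neither appliance can act before it is applied, so omitting earlier events is not in itself an error. The window also opens at use, which need not mean completed fitting; if use begins with the first step of application, extra assembly steps create no gap. Finally, the rate formula speaks of cases in a period over all ICU inpatients, so it is not certain that the numerator is confined to the window.

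Much of this stands. It rules out several stronger conclusions that a reader might draw:

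- *That some eligible patients have no time at risk.* This is possible under one reading of ④, but the documents do not establish it.
- *That patients reintubated later in the stay enter at a different stage.* The protocol does not mention reintubation, and the window is tied to tool use after surgery.
- *That the bias favours the new appliance, by two routes.* Slower fitting is an inference from the description, and the second route disappears (step 5 of the working).

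The reply does not remove the core. The background wording shows intent but fixes no moment for ④. That neither appliance acts before use does not justify a start that staff control and that may differ by arm. The doubt over the rate formula is a further reason to define the window and denominator together.

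**Conclusion.** The point holds as a low-severity improvement. It is established from the text that ④ has no time anchor and that the main-outcome window opens after allocation at an arm-dependent moment chosen by staff who know the arm. On the literal wording, unplanned extubations after allocation and before tool use are not counted.

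Bias follows only if time to tool use, or the risk during it, differs by arm. The protocol gives nothing from which to judge this, so size and direction are unknown. A shift in the risk ratio of roughly 2.5% to 5% either way rests wholly on the assumed 10-hour tube period, 15 to 30 minutes of extra delay and constant hazard. The effect is probably small, and it would be larger only if events cluster before tool use.

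**What to change.** 1. Reword ④ to: *endotracheal tube in place on arrival in the ICU after the index operation (or at randomisation, if that is later)*.
2. State in section 3.4 when allocation takes place. Randomisation alone cannot serve as the anchor until this is settled. If patients are allocated before surgery, nobody has a tube at that moment, and the window would include time before intubation.
3. In section 3.6, start the unplanned-extubation window at the same arm-independent time point as in ④. Count every event from then until tube removal in the assigned arm, whether or not the tool has yet been used.
4. Use as denominator all randomised patients who meet ④ at that point, in place of all ICU inpatients in an undefined period.

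The cost is a few sentences and one extra recorded time per patient. A few patients whose tube is already out at the anchor point would not be eligible. Nothing here changes when or how either appliance is applied.

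### Exclusion ③ (giving up treatment, or dying) has no time limit and, on its natural reading, removes patients for events after randomisation

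*Protocol*

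**What the plan says.** Section 3.3 gives three exclusions. The first two are baseline states: a history of mental illness, and a bleeding tendency or skin disease. The third is "voluntary abandonment of treatment or death in ③". The item number is displaced, the last preposition has no object, and no time is attached.

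The inclusion list in the same section asks for consent, for intubation during the ICU stay, and that before restraint "there was no joint dysfunction, edema, skin damage, etc. at the proposed restraint site". Section 3.4 then says that "the included subjects were randomly divided into control group and experimental group".

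The purpose in section 2 is to "study the effectiveness and safety of the new restraint appliance". Section 3.6 sets the observation window: "This study starts with the use of the protective restraint tool after surgery until the removal of the endotracheal tube". Under main outcome measures it defines the unplanned extubation rate as the number of cases divided by the "total number of ICU inpatients in the statistical period". Section 3.7 says that nursing adverse events, with other items, "were collected by the investigator through the electronic medical system and integrated nursing information platform". Anxiety, depression and comfort are scored early after waking and again "on the day the patient was pre-transferred out of the ICU".

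**The concern.** Death cannot be a screening finding in a patient who has consented, and giving up treatment normally happens after it has begun. Placed among the exclusions without a time limit, item ③ reads as an instruction to take out patients who were already allocated. Membership of the comparison would then depend on what happened after randomisation, which is what randomisation is meant to prevent. Unplanned extubation is the listed main outcome, and death or abandonment may follow it, so the patients removed may be the ones who had the event. The contrast could shift either way, and deaths and abandonments would disappear from a trial whose stated purpose includes safety.

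The denominator in section 3.6 is a second, separate problem. It is worded as a ward quality indicator and does not describe the patients of either arm.

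**Working it through.** The protocol states no event, death or abandonment rate, so there is no figure of its own to reproduce. The first step is a reading of the text. The others are illustrations on assumed inputs.

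**1. Order of events.** Consent, ICU intubation and a sound site before restraint are conditions of inclusion (3.3). Those included are randomised (3.4). Observation runs from first restraint to tube removal (3.6). An event in item ③ that befalls an included patient therefore comes, on the natural reading, after allocation. Nothing in the text limits it to an earlier time.

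**2. Effect on one arm's rate.** Let u be the true risk of unplanned extubation, q the share lost under item ③ among patients with the event, and s the share lost among those without it. With the lost removed from numerator and denominator:

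observed rate = u(1−q) / [u(1−q) + (1−u)(1−s)]

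- Assumed u = 0.10, q = 0.20, s = 0.03: 0.080 / (0.080 + 0.873) = 0.080/0.953 = 8.4%, against 10.0% with everyone counted. Per 1,000 patients, 20 of 100 events and 27 of 900 non-events are lost.
- Assumed u = 0.10, q = 0.03, s = 0.10: 0.097 / (0.097 + 0.810) = 0.097/0.907 = 10.7%. The rate can also rise.

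**3. Effect on the contrast with no true difference.** With equal u and equal s in the two arms, the observed odds ratio (experimental to control) reduces to (1−qE)/(1−qC). If q lies anywhere from 0 to m in each arm, the limits are 1−m and 1/(1−m). The risk ratios are at u = 0.10, s = 0.03.

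| m (assumed) | False odds ratio | False risk ratio |
|---|---|---|
| 10% | 0.90 to 1.11 | 0.91 to 1.10 |
| 20% | 0.80 to 1.25 | 0.82 to 1.22 |
| 50% (extreme) | 0.50 to 2.00 | 0.53 to 1.90 |

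Equal loss after the event in both arms gives an odds ratio of 1.00.

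**4. Sensitivity with few events.** The sample size in section 4 is not legible, so assume 50 per arm with 8 events on control and 4 on the experimental device. Two-sided Fisher tests give:

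- all kept: 16.0% v 8.0%, p = 0.357;
- one experimental patient with the event removed: 3/49 = 6.1%, p = 0.200;
- two removed: 2/48 = 4.2%, p = 0.092;
- three removed: 1/47 = 2.1%, p = 0.031.

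This is deliberately one-sided. It shows how much a few exclusions can matter when events are sparse, and does not forecast what will happen here.

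**5. The denominator, taken separately.** Six events in an arm of 50 (assumed) are 6/50 = 12.0%. Over an assumed 300 ICU inpatients in the period they are 6/300 = 2.0%. The mismatch arises because the stated total takes in ICU patients outside the trial, so it remains if item ③ is deleted.

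**The case against.** The strongest objection is that the clause is damaged. A time qualifier may have been lost in translation. Consent and preoperative awareness are among the inclusion conditions, so enrolment may begin before surgery, and death or withdrawal before first restraint would then be an ordinary screening loss. The time of randomisation is not stated, and no sentence says that allocated patients leave the analysis. This stands as far as it goes: removal after allocation is inferred, and the first step must be to clarify the clause. It does not dispose of the point, because the ICU-stage inclusion conditions and the order of sections 3.3 and 3.4 favour the later reading.

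It may also be said that analysis sets belong in the SAP. The absence of an analysis-set statement here is indeed no fault. The criticism is of an exclusion that the protocol itself states.

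Some stronger readings are tempting and are not supported:

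- A reader might take the ICU-inpatient denominator as proof that item ③ contradicts the main outcome definition. It is a ward-level formula that would misfit the trial anyway, and it says nothing about how item ③ operates.
- A reader might take abandonment to mean stopping the assigned restraint device. Elsewhere the protocol uses the word treatment for ICU care, so leaving care is the more natural sense.
- A reader might infer that the exclusion favours the new device. Nothing in the document indicates a direction.

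Finally, a death after tube removal arguably falls outside the observation window. That is unsettled, since section 3.7 collects data up to transfer from the ICU. Item ③ as worded would still reach such a patient, whose extubation outcome is already known.

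**Conclusion.** The point holds in a conditional form. Item ③ has no stated timing and, on its natural reading, excludes patients for events after allocation. If applied so, it can bias the unplanned extubation contrast in either direction and discard events relevant to safety. The size and direction cannot be derived from the protocol. The figures above rest wholly on assumed risks, losses and arm sizes, and the 50% row and the p-value sequence are chosen extremes. The section 3.6 denominator is a separate defect that needs correction whatever is decided on item ③. Both should be fixed. Confidence is medium because of the state of the text.

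**What to change.** - Limit exclusions in section 3.3 to conditions known before allocation. If item ③ was meant for losses before allocation, say so and count those patients as screening losses. Otherwise delete it.
- In section 3.6, make all randomised patients, in their assigned arm, the denominator of the unplanned extubation rate.
- Count unplanned extubations from the records up to tube removal, death or the end of available records.
- Report deaths and abandonments by arm.

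The cost is protocol wording and a little more reporting, since section 3.7 already draws nursing adverse events from electronic systems. The downside is that some later anxiety, depression and comfort scores, due around transfer from the ICU, will not exist for these patients and must be reported as missing. The reported rates and the contrast may move either way.

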#### 4, and the sample size calculation

The test group and the control group were selected separately 5 For example, patients.

All records concerning the identity of the subject are kept confidential and are not publicly available beyond the extent permitted by the relevant laws and / or regulations.

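### Section 3.4 allocates by coin throwing and 3.1 by random number table; free tosses cannot guarantee the equal arms of the sample size section, and leave no list that can be checked

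*Protocol*

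**What the plan says.** Three places in the protocol bear on how patients reach an arm.

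- Section 3.1: "This study used random number table to divide the subjects into control and experimental groups".
- Section 3.4, on recruitment: "This study used the convenient sampling method to select the research subjects". On allocation, it adds that "the included subjects were randomly divided into control group and experimental group according to the coin throwing method".
- The sample size section (numbered 4): "The test group and the control group were selected separately 5 For example, patients". The number is damaged and a digit may be lost, but one figure is applied to both groups, so equal arms are the natural reading.

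Sections 3.4 and 3.5 also show that the two arms can be told apart at the bedside. In 3.4 the control arm receives a sponge belt, whereas "the experimental group used the restraint appliance as the new restraint appliance"; 3.5 describes the first as a wrist or ankle band and the second as an assembly of elbow brackets with a glove.

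The protocol gives no rule for an arm that has reached its number. It does not say who selects patients or who throws the coin.

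**The concern.** Sections 3.1 and 3.4 name different allocation methods, and coin throwing does not fit a fixed number per arm. Independent tosses produce arms of random size. To end with the planned number in each arm, someone must either accept the imbalance or stop tossing once one arm is full and send everyone else to the other. In the second case the remaining allocations are certain before the patient is approached.

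A coin also leaves no sequence fixed in advance. A toss that was repeated because its result was unwelcome cannot be told from a proper one.

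Either weakness matters more when entry is discretionary and past allocations are visible. Convenience selection lets the person enrolling decide whom to approach and when. Unplanned extubation, a main outcome in 3.6, includes self-extubation, which plausibly depends on how agitated the patient is. Agitation is not among the baseline items listed under data collection, so on those items alone an analysis could neither detect nor adjust for a difference in it between the arms.

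**Working it through.** **Inputs**
- Toss probability: 0.5 for each arm, independent (assumed; not stated in 3.4).
- Equal target n per arm, total N = 2n (sample size section). Because the figure is damaged, n = 5 (the legible digit), 50 and 100 are shown. All three are assumptions.

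The sample size section gives no inputs from which its figure could be rebuilt, so there is no stated figure to reproduce. The check concerns only whether the allocation method fits an equal target.

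**Step 1: chance that free tosses give exactly equal arms**

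P(equal) = C(N, n) / 2^N

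- N = 10: 252 / 1024 = 0.246
- N = 100: 0.080
- N = 200: 0.056

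The central 95% range for the size of one arm is 2 to 8, 40 to 60 and 86 to 114 respectively.

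**Step 2: what the imbalance costs**

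For a comparison of two arms with similar variance, the information relative to a 50:50 split is 4p(1 − p), where p is the share in one arm. At the edge of the 95% range:

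- N = 10, split 2:8: 4 × 0.2 × 0.8 = 64%
- N = 100, split 40:60: 4 × 0.4 × 0.6 = 96%
- N = 200, split 86:114: 4 × 0.43 × 0.57 = 98%

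**Step 3: what happens if equality is forced by closing the full arm**

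The first arm fills at toss t with probability 2 × C(t − 1, n − 1) / 2^t, for t = n to 2n − 1. The remaining 2n − t allocations are then determined. For n = 5:

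| t | Probability | Determined allocations |
|---|---|---|
| 5 | 0.0625 | 5 |
| 6 | 0.1563 | 4 |
| 7 | 0.2344 | 3 |
| 8 | 0.2734 | 2 |
| 9 | 0.2734 | 1 |

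The expected number is 0.3125 + 0.6250 + 0.7031 + 0.5469 + 0.2734 = 2.46. The closed form N × C(N, n) / 2^N agrees: 10 × 0.2461 = 2.46.

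- N = 10: 2.46 (24.6%)
- N = 100: 7.96 (8.0%)
- N = 200: 11.27 (5.6%)

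At least one allocation is always determined. At least two are determined with probability 0.727 when n = 5 and 0.92 when n = 50.

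**Step 4: the conflict between 3.1 and 3.4**

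A random number table can be used without restriction, in which case steps 1 to 3 apply unchanged, or to prepare a list with equal arms, in which case they do not. Section 3.1 does not say which. Reconciling the two sections by name alone would therefore leave the equal-arms question open.

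**The case against.** The strongest objection is that the protocol never says a full arm is closed. Free tosses are unpredictable, and 3.4 places the toss after inclusion. Simple randomisation towards a per-arm target is an accepted design, and the chi-square, Fisher, t and non-parametric tests in the statistical analysis section do not need equal arms. This stands: the foreseeability in step 3 is conditional, and the imbalance in step 2 is minor unless the trial is very small.

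A reader might go further and infer any of the following, none of which the documents support.

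- *Coin throws cannot produce equal arms.* They can, by chance; they cannot guarantee them.
- *Staff of the department that developed the device will steer calmer or more agitated patients to one arm.* The background section says the department developed the device, but nothing says who recruits. Nor is it stated when enrolment takes place relative to surgery, so agitation may not yet be apparent.
- *The trial plans five patients per arm.* The sentence is damaged, and that digit cannot be relied on.

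It can also be said that permuted blocks have determined tails of their own. If the block size is known, on average 4/3 of every 4 allocations (33%) or 1.5 of every 6 (25%) are foreseeable, which exceeds the forced tail at 100 patients. This is correct for known, fixed blocks, and is why the sizes must be mixed and undisclosed.

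**Conclusion.** The point holds in a limited form. The protocol names two allocation methods. The one in 3.4 does not secure the equal arms that the sample size section implies, and it leaves no pre-set sequence that can be checked. Exact equality has a chance of about 25%, 8% and 6% at assumed totals of 10, 100 and 200. By itself that costs little precision except at the smallest size.

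The more serious consequence is selection bias. It arises only if a full arm is closed, or if tosses can be repeated unseen. The protocol provides for neither and guards against neither. If a full arm is closed, about 25%, 8% and 6% of allocations would be foreseeable on average, between visibly different devices and with patients chosen by convenience.

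These figures assume fair, independent tosses and equal targets. The direction of the conclusion does not depend on the damaged number. The change is worth making because it costs almost nothing and the bias could not be reliably repaired afterwards.

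**What to change.** - State one method in both 3.1 and 3.4: a computer-generated list in randomly permuted blocks of mixed, undisclosed sizes, prepared and held by a team member who does not enrol.
- Hold the allocations in numbered, sealed, opaque envelopes, each opened only after eligibility and consent have been recorded.
- Replace convenience selection in 3.4 by consecutive screening of eligible patients, with a log of those screened, enrolled and not enrolled.
- Restore the number per arm in the sample size section, so that the list can be built to it.

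The cost is a short amendment, preparation of the list and envelopes, and upkeep of the log; no extra patients or visits are needed. Some predictability remains at block ends because the devices can be told apart. Mixed, undisclosed block sizes limit it but do not remove it.
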